### 9.2.1. Aim 2 Sample Size Considerations

Based on our preliminary data and a national survey, we anticipate 28% RSV vaccine uptake in our text-only arm (20% with no intervention and 8% increase with text). Assuming complete data for the primary outcome of vaccine uptake reported by CAIR, the medical record, or proof of vaccination from a pharmacy and  $\alpha=0.05$ , our sample size of N=200 per arm will conservatively

provide a minimum detectable ITT effect size of 10%. Assuming CHWs will be able to reach 90% of participants assigned to the counseling arm, our sample will be able to provide a minimum detectable ATT of 10.9%; if participants assigned to counseling are particularly hard to reach and only 80% take part in CHW counseling, we will be able to provide a minimum detectable ATT effect 12.3%.

Statistical power for secondary outcomes will depend on participation in the 60-day follow-up survey. If 10% of participants are lost to follow-up, the minimum detectable effects increase to 10.6% for ITT, 11.5% for ATT if 90% of intervention arm participants receive counseling and 12.9% for ATT if 80% of intervention arm participants receive counseling. Under a setting of high loss to follow-up, where 20% of participants in both arms are not reached for a follow-up survey, the minimum detectable effects increase to 11% for ITT, 12.2% for ATT if 90% of intervention arm participants receive counseling and 13.7% for ATT if 80% of intervention arm participants receive counseling.

Estimated treatment effects for all outcomes will be improved with statistical modeling with TMLE.

In a nested secondary pre-post analysis we will compare the proportion of people who received the RSV vaccine prior to the text-message to 30 days after the text.

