**In 2025 the Centers for Disease Control (CDC) and the Advisory Committee on Immunization Practices (ACIP) updated their recommendations and all adults 50 years older are eligible for one dose of the RSV vaccine.** They also uniformly recommend one RSV vaccination for (1) adults 75 years and older and (2) adults 50-74 years old who have an increased risk of severe RSV disease. Persons who are considered at increased risk for RSV are those with: cardiovascular disease (e.g hypertension, coronary artery disease), lung disease (e.g COPD, asthma), advanced chronic kidney disease, diabetes, liver disorders, neurologic or neuromuscular conditions, hematologic disorders, moderate or severe immune compromise, frailty, people who reside in nursing homes, people with chronic medical conditions or risk factors that a healthcare provider determines might increase risk of severe disease due to respiratory infections.

**Vaccine hesitancy is a major threat to the equitable uptake of the new Respiratory Syncytial Virus (RSV) vaccines.** Since the introduction of the new RSV vaccine for older adults in 2023, uptake has been low, and significant disparities have already emerged.

According to the CDC, as of May 2024, only 24% of adults over the age of 60 have received the vaccine, with uptake differing by race-ethnicity (14.5% among non-Latino, 20.7% Black, 26.5% non-Latino White), insurance status (7.7% uninsured vs. 25% insured) status, and income level (15.5% for people below the national poverty level vs. 27.9% for those above the national poverty level). Multi-level, community-based interventions are needed to address the three components of RSV vaccine hesitancy: *confidence* in the safety and efficacy of the vaccine, *complacency* towards vaccine uptake, confidence in the safety and efficacy of this new vaccine, and *convenience* in accessing the vaccine.

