**Behavioral nudges with text messages can increase vaccine uptake.** In behavioral economics, nudges are small interventions or alterations in the environment that make it more likely that an individual will make a particular (preferred) choice. A text message nudge can address two barriers. First, it serves as a prompt to make the recipient aware a vaccination is due and to follow through on vaccination intentions. Second, it can provide information about how and where to schedule appointments. Text messages interventions from large health systems have demonstrated success for flu vaccination, childhood vaccines and COVID-19, with a boost in vaccination by 4%-8%. Latinos, especially those who are uninsured, are largely left out of these studies. For example, in a large text-message study in a health system in Los Angeles, Latinos comprised only 10% of the study population despite being 48.6% of the population. While text messaging reminders are a promising intervention, we need to improve the reach of this tool to patients who are uninsured or not on digital health system portals. To date, aside from our preliminary data, *there are no studies focusing on text messaging interventions with texts originating from community-based organizations.*

**Social networks can exert positive influences on vaccine uptake.** Social contagion theory describes the process whereby a person adopts the health behaviors or attitudes of their social network A scoping review on social networks and vaccination highlight three main areas of influence that motivate our proposed work: (1) Individuals were more likely to have a positive attitude to vaccination and higher uptake if their friends or family held positive beliefs about vaccination (2) Individuals were more likely to get vaccinated or perceive a vaccine as effective

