**Table 4: Inclusion and Exclusion Criteria**

Study	Inclusion Criteria	Exclusion Criteria
Aim 1		
RSV Vaccine Confidence Survey	(a) Adult age $\geq 18$ years (b) Speaks Spanish or English	Not able to provide informed consent
Community Advisory Groups for Adaptation of Intervention	1. Group 1: a. age $\geq 60$ years b. speaks Spanish or English c. self-identifies as Latino/a/e/x and/or indigenous group from Latin America d. lives or works in San Francisco County or Daly City and able to come to in-person meetings in San Francisco 2. Group 2: a. age 18-50 b. speaks Spanish or English c. Self-identifies as Latino/a/e/x and/or indigenous group from Latin America d. lives or works in San Francisco or Daly City and able to come to in-person meetings in San Francisco	Not able to provide informed consent  Planning on moving out of San Francisco or Daly City area in 12 months
In Depth Interviews (Aim 1)	(a) Self-identifies as Latino/a/e/x and/or indigenous group from Latin America (b) Speaks Spanish or English (c) Age $\geq 18$ years	Not able to provide informed consent
Aim 2 'Motivate Trial'	Inclusion Criteria: (a) Age $\geq 50$ years (b) Self-identify as Latino/a/x and/or indigenous groups from Latin America	(a) Intent to move outside of San Francisco in the next year

	
 
(c) Eligible for RSV vaccination per current CDC/ACIP recommendations*
 
(c) Fluent in Spanish or English
 
(d) Has not received the RSV vaccine
 
(e) Has a cell phone
 
(f) Lives or works in San Francisco or Daly City
 
(f) Able to provide informed consent
 
 
* CDC/ACIP Eligibility for RSV Vaccination:
 
 
(1) Age 75 years and older
 
(2) Age 50-74 and one of the following medical comorbidities: cardiovascular disease (e.g. coronary artery disease), lung disease (e.g. COPD, asthma), advanced chronic kidney disease, diabetes, liver disorders, neurologic or neuromuscular conditions, hematologic disorders, moderate or severe immune compromise
 
	
 
(b) Nursing home resident
 
(c) Household member participating in Aim 1 or 2
 
(d) Unable to provide consent
 

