## 9.2. Aim 2 (Motivate Trial) Statistical Considerations

**Study Design:** Two-arm randomized type-1 effectiveness-implementation individually randomized trial.

**Analysis Plan.** We will compare the primary outcome of RSV vaccine uptake within 60 days between the two study arms using two broad statistical approaches: unadjusted analyses to explore average treatment effects and model adjusted estimates to reduce variance and examine effects for subpopulations. First, we will examine the intention-to-treat (ITT) effect, over all participants, for the primary outcome of vaccine uptake using the Fisher exact test. To account for participants which the CHW may not be able to reach, we will examine the average treatment effect on the treated (ATT). Second, we will use targeted maximum likelihood estimation (TMLE), a pre-specified approach to data-adaptively adjust for stratified randomization factors and additional baseline predictors of the outcome in order to improve precision. RSV vaccine uptake will be ascertained through the California Immunization Registry, the medical record, or proof of vaccination from a pharmacy. Using an analogous approach, we will also compare intervention effectiveness on pre-specified secondary outcomes and within pre-specified subgroups: baseline high vaccine hesitancy, low trust of healthcare system, low acculturation (score<3.0), sex. These will be augmented by predictor analyses to elucidate risk factors for poor vaccine uptake, overall and by arm and exploratory machine learning analysis for treatment effect heterogeneity. Additionally, we will examine pathways of intervention action (i.e. direct and indirect effects) using formal mediation analyses, considering mediation by post-baseline trust and perceived benefits in the vaccine. Both predictor and mediation analyses will use TMLE.

**Implementation Outcomes:** We will calculate implementation outcomes using the RE-AIM framework for each, through quantitative and qualitative analyses.

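### Motivate sample size (9.2.1): the 28% text-only rate has no stated window or risk set, and the 10-point detectable effect does not follow from 28% and 200 per arm

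*Protocol*

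**What the plan says.** Protocol section 9.2.1 builds the control rate in two steps: "we anticipate 28% RSV vaccine uptake in our text-only arm (20% with no intervention and 8% increase with text". The basis is given as "Based on our preliminary data and a national survey", with no reference, period or population. With complete outcome data, a significance level of 0.05 and 200 per arm, the design is said to "provide a minimum detectable ITT effect size of 10" percent. Effects on the treated of 10.9 and 12.3 points are given for 90% and 80% reach of counselling. No power is named for this trial; 80% appears only in section 9.3.1, for the Activate trial.

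Three other places bear on the rate:

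- **Endpoint (section 9.2):** "We will compare the primary outcome of RSV vaccine uptake within 60 days between the two study arms".
- **Risk set (Table 4, Aim 2):** "Has not received the RSV vaccine".
- **National uptake (section 1.1):** "as of May 2024, only 24% of adults over the age of 60 have received the vaccine". Group figures run from 14.5% to 26.5%.

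The text effect reported in section 1.2 comes from messages sent by large health systems, "with a boost in vaccination by 4%-8" percent. The plan adds 8 points, the top of that range.

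**The concern.** A planning rate has to describe the same event, window and population as the endpoint. Here the event is a first RSV vaccination within 60 days in someone still unvaccinated at entry. The only national uptake figures in the protocol measure something else: the share ever vaccinated, accumulated over many months, which counts as successes the very people whom Table 4 excludes. A no-intervention rate of 20% in two months looks high beside 24% reached over the whole period since introduction.

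The rate matters because it fixes both the detectable difference and what that difference means. Ten points on 28% is a modest relative gain; ten points on a much lower rate is a large one. A reader of section 9.2.1 also needs to know whether 10 points can be detected with conventional power at the rate the plan itself adopts.

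**Working it through.** **1. Reproducing the stated 10 points.** Inputs from section 9.2.1: control rate 0.28, n = 200 per arm, level 0.05. Assumptions: two-sided test, 80% power, normal approximation with pooled variance under the null.

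- Null standard error at the mean rate of 0.33: √(2 × 0.33 × 0.67 / 200) = 0.0470. Critical difference: 1.96 × 0.0470 = 0.0922.
- Standard error under the alternative: √((0.28 × 0.72 + 0.38 × 0.62) / 200) = 0.0468.
- Power for 28% against 38%: Φ((0.10 − 0.0922) / 0.0468) = Φ(0.17) ≈ 57%. Exact power for the planned Fisher test is 53%.
- Solving for 80% power gives a detectable difference of 13.3 points. A 10-point difference would need 346 per arm.
- One-sided testing does not recover the figure either: power is 69% (Fisher 65%) and the detectable difference is 11.7 points.

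**2. What the printed figures do match.** The half-width of a 95% interval for a difference at p = 0.5 is 1.96 × √(0.5 / n). Dividing by the reach gives the effect on the treated.

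| n per arm | Half-width (stated ITT) | ÷ 0.9 (stated) | ÷ 0.8 (stated) |
|---|---|---|---|
| 200 | 9.8 (10) | 10.9 (10.9) | 12.25 (12.3) |
| 180 | 10.3 (10.6) | 11.5 (11.5) | 12.9 (12.9) |
| 160 | 11.0 (11) | 12.2 (12.2) | 13.7 (13.7) |

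All but the 10.6 agree. A true difference equal to that half-width is detected with about 50% power. The 28% appears not to enter these figures at all. This is a match of numbers; the protocol does not give its method.

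**3. Is 20% in 60 days compatible with section 1.1?** Assume a constant rate of 20% per two months in the unvaccinated. Coverage after m months is 1 − 0.8^(m/2): 43% after 5 months and 67% after 10. Introduction at some time in 2023 puts May 2024 between 5 and 17 months later, and the protocol reports 24%.

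In the other direction, the 60-day rate implied by coverage c after m months is 1 − (1 − c)^(2/m). For c = 14.5% it is 6.1% (m = 5) to 1.8% (m = 17). For c = 24% it is 10.4% to 3.2%. Adding 4 to 8 points for the text gives a text-only rate of roughly 6% to 18%. The 14.5% carries a label in section 1.1 that appears to be a slip, so it serves only as a lower bound.

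**4. What other control rates would mean** (200 per arm, two-sided 5%, same method):

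| Control rate | Power for +10 points | +10 points as a ratio | 80%-power difference | As a ratio |
|---|---|---|---|---|
| 8% | 85% | 2.25 | 9.3 points | 2.2 |
| 10% | 80% | 2.00 | 10.0 points | 2.0 |
| 15% | 71% | 1.67 | 11.3 points | 1.75 |
| 28% | 57% | 1.36 | 13.3 points | 1.5 |

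**The case against.** Section 9.2.1 does not claim to use national coverage. It cites the team's own preliminary data and an unnamed survey, neither shown, and 20% equals none of the figures in section 1.1. A reader might infer that cumulative coverage was mistaken for a 60-day rate. The documents do not support that as a fact, because the origin of the 20% cannot be traced.

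The conversion in step 3 is also rough. RSV is seasonal, so a constant rate is doubtful. The 24% describes adults over 60 in general, whereas the trial enrols consenting, compensated adults who are 75 or older, or 50 to 74 with a listed condition. The 8 points may rest on the team's own texting data, and the text-only arm also gets a flyer from a health worker and a hotline number. All of this stands: the documents yield no correct 60-day rate, and 28% cannot be called wrong.

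A reader might further infer that a lower true rate leaves the trial short of power for its stated effect. On the absolute scale that the plan uses, the reverse holds, as the step 4 table shows. Nor does the plan set a relative gain as its target; 1.36 is only the arithmetic of 38/28.

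Two defences of the 10 points fail. The section calls its figure conservative, which would fit the use of p = 0.5, but p = 0.5 with 80% power gives (1.96 + 0.84) × √(0.5 / 200) = 14.0 points. It also expects gains from targeted maximum likelihood estimation. Bringing 346 per arm down to 200 would take a variance reduction of about 42% (1 − 200/346), and the protocol quantifies no gain. The first intention-to-treat comparison is an unadjusted Fisher test.

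**Conclusion.** Two faults in section 9.2.1 hold.

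- **The control rate is unsupported for this endpoint.** The window and risk set of the 20% are not stated. Read as a 60-day rate in unvaccinated adults, it sits badly with the protocol's only national uptake figures. It is probably too high; by how much cannot be said. The 6% to 18% range rests on a constant rate and an assumed 5 to 17 months, and is illustrative.
- **The 10-point figure does not follow from the plan's own inputs.** At 28% and 200 per arm, power for 10 points is about 57% and the 80%-power difference is 13.3 points. This rests on a two-sided test and 80% power, neither stated for this trial. It does not depend on the first fault.

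A lower base rate would not in itself weaken the trial for 10 absolute points. It would change what those points mean, from 1.36-fold at 28% to 1.67-fold at 15% and 2-fold at 10%. The present text does not let a reader see this.

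**What to change.** In section 9.2.1:

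- State the source, time window and vaccination status behind the 20%. If the preliminary data give a 60-day rate among unvaccinated eligible adults, use it. Otherwise present 28% as one assumption within a range, with the text effect taken over 4 to 8 points.
- Name the power and whether the test is two-sided.
- Replace the 10-point figure with 80%-power differences over a range of control rates, absolute and relative: for example 9.3 points (2.2-fold) at 8%, 10.0 (2.0-fold) at 10%, 11.3 (1.75-fold) at 15% and 13.3 (1.5-fold) at 28%.
- Recompute the effects on the treated from those values. With the same division by reach, 13.3 points becomes 14.8 at 90% (13.3 / 0.9) and 16.6 at 80% (13.3 / 0.8). Put the figures for 10% and 20% loss to follow-up on the same basis.

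The cost is a rewritten paragraph and a less favourable stated figure at 28%. No extra participants are needed.

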#### **9.3.1. Aim 3 Sample size considerations**

As with the secondary outcomes for Aim 2, statistical power will depend of participation in the 60-day follow-up interview. Assuming 10% attrition for the 175 participants in each arm, we will be able to detect a minimum ITT effect of 11% for any binary outcomes. For our primary outcome, assuming a standard deviation (Standard Deviation) of 0.3 for the proportion of adults contacted, with 175 participants/arm we will have 80% power (using  $\alpha=0.05$ ) to detect at least a 10% absolute increase (e.g. from 30% to 40%) in the average proportion of older adult contacts with whom RSV vaccination was discussed.

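### The Motivate minimum detectable effects carry no power term: the stated 10 points has 53–57% power, and 80% power needs about 13.3 points

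*Protocol*

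**What the plan says.** For Motivate, section 9.2.1 says "we anticipate 28% RSV vaccine uptake in our text-only arm". With alpha 0.05, complete outcome data and 200 per arm, it says the sample will conservatively "provide a minimum detectable ITT effect size of 10" percent. The corresponding ATT figures are 10.9% if 90% of the counselling arm is reached and 12.3% if 80% is reached.

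For survey-based secondary outcomes the section says "Statistical power for secondary outcomes will depend on participation in the 60-day follow-up survey". At 10% loss, "the minimum detectable effects increase to 10.6% for ITT, 11.5% for ATT if 90% of intervention arm participants receive counseling", and 12.9% if 80% receive it. At 20% loss, "the minimum detectable effects increase to 11% for ITT, 12.2% for ATT if 90% of intervention arm participants receive counseling", and 13.7% if 80% receive it.

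For Activate, section 9.3.1 assumes 10% attrition from 175 per arm and says "we will be able to detect a minimum ITT effect of 11% for any binary outcomes". For the continuous primary outcome it assumes an SD of 0.3 and says "with 175 participants/arm we will have 80% power" for a 10-point increase.

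Section 9.2 plans the Motivate intention-to-treat comparison "for the primary outcome of vaccine uptake using the Fisher exact test".

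The 80% for the Activate primary outcome is the only power named in section 9. No power is attached to any of the ten binary figures, and no sidedness is given.

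**The concern.** A minimum detectable effect means something only with a power attached. Section 9.2.1 attaches none, yet calls its figure conservative and goes on to discuss statistical power. Section 9.3.1 then uses detection in the ordinary 80%-power sense for one outcome, directly after a binary figure that does not appear to use it. A reader will assume conventional power throughout.

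These figures are the protocol's only sample-size justification for the Motivate primary outcome. If they overstate the trial's sensitivity, funders and the ethics board are misinformed. A null result could also be read as ruling out effects that the trial would miss almost half the time.

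**Working it through.** **Inputs.** Control uptake 28%, alpha 0.05, 200 per arm, counselling reach 90% or 80%, loss 0, 10% or 20% (n = 200, 180, 160), all from section 9.2.1. Activate: 175 per arm less 10% = 157.5, SD 0.3, from section 9.3.1. Fisher test from section 9.2. Two-sided testing is assumed because the protocol does not say.

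**1. Reproducing the stated figures.** The protocol gives no formula. The one that fits is 1.96 × √(0.5/n), divided by reach for the ATT. At n = 200, for example, 1.96 × √0.0025 = 9.80 points, 9.80/0.9 = 10.89 and 9.80/0.8 = 12.25.

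| n per arm | Computed ITT / ATT 90% / ATT 80% | Stated |
|---|---|---|
| 200 | 9.80 / 10.89 / 12.25 | 10 / 10.9 / 12.3 |
| 180 | 10.33 / 11.48 / 12.91 | 10.6 / 11.5 / 12.9 |
| 160 | 10.96 / 12.17 / 13.70 | 11 / 12.2 / 13.7 |
| 157.5 (Activate) | 11.04 | 11 |

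Nine of ten agree to rounding. The exception, 10.6, also fails against its own companions: 11.5 × 0.9 = 10.35 and 12.9 × 0.8 = 10.32.

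The expression is the 95% half-width at p = 0.5, with z for power equal to zero. The 28% does not seem to enter: at 28% in both arms the half-width would be 1.96 × √(2 × 0.28 × 0.72/200) = 8.8 points.

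**2. Power at the stated figures.** With p = 0.5 variance, power = Φ(effect/√(0.5/n) − 1.96), with ATT figures multiplied back by reach. For 10 points at n = 200 this is Φ(0.10/0.05 − 1.96) = Φ(0.04) = 52%. Over all ten figures it runs from 50% to 52%. Starting from 28% (pooled two-proportion z-test) it runs from 54% to 57%.

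**3. The primary comparison, 28% against 38%, 200 per arm.** Power is 56.7% by the pooled z-test and 52.7% by full enumeration of the two-sided Fisher test.

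**4. What 80% power would give from 28%, n = 200.** Solving the pooled z-test power for the difference gives 13.29 points. The ATT is 13.29/0.9 = 14.8 and 13.29/0.8 = 16.6. With Fisher the ITT value is 13.7, and the ATT values are 15.3 and 17.2.

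**5. Sample size for 10 points at 80% power.** n = [1.96√(2 × 0.33 × 0.67) + 0.8416√(0.28 × 0.72 + 0.38 × 0.62)]² / 0.10² = 345.9, so 346 per arm. Exact Fisher power is 77.7% at 346 and 80.1% at 365.

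**6. The Activate continuous outcome.** (1.96 + 0.8416) × 0.3 × √(2/n) gives 9.0 points at 175 per arm and 9.5 at 157.5. Power for 10 points is 88% and 84%. The stated 10 points holds.

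**The case against.** - **The half-width formula is inferred.** True: the protocol prints no formula. The stated ITT 10 is also rounded more coarsely than its neighbours, and 12.3 matches only with z taken as 1.96. The inference still rests on one rule giving nine of ten figures, and no 80%-power calculation at 28% comes close. The power shortfall in steps 2 and 3 does not depend on the inference.
- **The protocol never claims 80% power for Motivate.** Also true, so 13.3 does not correct a stated 80% claim. The fault is calling an effect detectable, and conservatively so, when it would be detected only slightly more often than not.
- **The hypothesis is directional, so the test could be one-sided.** At one-sided 0.05, power at 10 points is 69% and the 80%-power effect is 11.7 points. Neither supports 10.
- **TMLE adjustment will improve precision.** The 53–57% is for the unadjusted test. Matching 346 per arm with 200 would need a variance reduction of about 1 − 200/346 = 42%. The protocol quantifies no gain, and the stated figures do not include one.
- **Nothing in the analysis becomes invalid.** Agreed, and the protocol does not name 10 points as its smallest worthwhile effect. What is wrong is the stated sensitivity of the primary comparison.

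**Conclusion.** The concern holds. The Motivate sample-size statement misdescribes what 200 per arm can detect. The 10-point effect has 53% power (Fisher) to 57% (normal approximation), against 13.3 points (13.7 with Fisher) at 80% power. The other binary figures in sections 9.2.1 and 9.3.1 have the same defect, and 10.6 is internally inconsistent as well.

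This assumes a two-sided 0.05 test, 28% control uptake, complete primary data and no covariate adjustment. The 80% benchmark is taken from the Activate primary outcome, whose own statement is sound.

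**What to change.** State power and sidedness in sections 9.2.1 and 9.3.1, then do one of two things: restate the binary figures at that power, or keep 10 points and say that it has 53–57% power. Correct 10.6 so that it agrees with its ATT companions.

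At 80% power, two-sided 0.05, the values in points are (ITT / ATT at 90% / ATT at 80%):

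| n per arm | From 28% control | p = 0.5 variance |
|---|---|---|
| 200 | 13.29 / 14.77 / 16.61 | 14.01 / 15.56 / 17.51 |
| 180 | 14.04 / 15.60 / 17.55 | 14.77 / 16.41 / 18.46 |
| 160 | 14.93 / 16.59 / 18.66 | 15.66 / 17.40 / 19.58 |
| 157.5 (Activate, ITT) | 15.05 | 15.79 |

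The Motivate primary outcome should use the 28% column, or the Fisher values 13.7 / 15.3 / 17.2. Most survey-based secondary outcomes and the Activate binary outcomes have no stated control rate, so the p = 0.5 column suits them. If 28% is assumed for them instead, the text should say so. Name the basis beside each series, so that a change of variance assumption is not read as an effect of attrition. The Activate continuous statement needs no change.

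The cost is protocol wording and less favourable printed figures. The test, the design and the number of participants do not change.
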